An intent-to-treat analytic approach will be employed. Multiple imputation will be utilized for subjects who discontinue during the study and do not complete the post-treatment assessment. Multiple imputation is desirable because instead of filling in a single value for each missing data point, each missing value is replaced with a set of plausible values, creating multiple imputed datasets. These datasets are then analyzed using standard procedures (that would be appropriate for a single, complete dataset), and results from the multiple data sets are combined into one set of results. The SAS procedures MI and MIANALYZE will be used for creating and analyzing multiple imputed data, resulting in statistically valid results that appropriately reflect the uncertainty due to missing values.

Multiple imputation is a useful method for analysis of datasets with data that are plausibly missing at random (MAR). Missing values rarely occur completely at random (MCAR). Instead, missing values are typically based on other variables, so they are MAR. During the multiple imputation process, the analyst should use all observed variables available in predicting missing values (even variables not used in analysis). If these variables are useful for predicting missing values, the multiple imputation increases power. Furthermore, by using an exhaustive set of predictor variables, the multiple imputation process creates a largely MAR dataset. Thus, multiple imputation can convert missing not at random (MNAR) data to MAR.

Simulation was used to determine sample size needed for analyzing multiple imputed datasets. We assume N=90 completers in each group, so a simulated dataset with N=180 subjects was created. Change in PAPA MDD severity sum scores were generated assuming normally distributed scores with a SD of 4.69 (pooled SD from our pilot RCT) and a mean difference in change scores in the two groups of 2.5. The demographic variables gender, age, race, family income, parental education level, and parental marital status were also included in this dataset. To simulate demographic characteristics, complete demographic profiles from the subjects in our pilot RCT were drawn with replacement 180 times and randomly assigned to the 180 simulated cases. A general linear model of change in PAPA MDD severity sum score by group was conducted for this simulated dataset.

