To address differential dropout and its impact on power, we assume a 25% drop-out rate in the PCIT-ED group and a 30% drop-out rate in the WL group. So 25% and 30% of the simulated PCIT-ED and WL subjects' MDD severity sum change scores were set to missing, respectively, using a random number generator. Because the simulated missingness was random, missing values are not predicted by anything, so data are missing completely at random (MCAR). This should be realistic for the multiple imputation power analysis that follows.

The SAS v9.2 MI procedure was used to create multiple imputed datasets with MDD severity sum change scores based on the simulated demographic variables in the dataset. Multiple imputation was conducted 10 times, with 10 imputed datasets created. The SAS v9.2 MIANALYZE procedure was then used to run a general linear model of change scores by group for each set of multiple imputed datasets. Table 5 shows the results of the general linear model in the complete simulated dataset and then each of the 10 multiple imputed datasets.

Dataset	Estimate	SE	SE ²	t	p
Complete Simulated Dataset	-2.278	0.729	0.532	-3.12	0.0021
Multiple Imputed Dataset 1	-2.307	0.745	0.555	-3.10	0.0020
Multiple Imputed Dataset 2	-1.951	0.855	0.731	-2.28	0.0241
Multiple Imputed Dataset 3	-2.090	0.569	0.756	-2.40	0.0182
Multiple Imputed Dataset 4	-2.121	0.848	0.718	-2.50	0.0137
Multiple Imputed Dataset 5	-2.063	0.816	0.666	-2.53	0.0122
Multiple Imputed Dataset 6	-1.894	0.796	0.633	-2.38	0.0178
Multiple Imputed Dataset 7	-2.220	0.824	0.679	-2.69	0.0078
Multiple Imputed Dataset 8	-2.079	0.846	0.715	-2.46	0.0152
Multiple Imputed Dataset 9	-2.121	0.850	0.723	-2.49	0.0141
Multiple Imputed Dataset 10	-2.124	0.845	0.714	-2.51	0.0128
Mean	-2.097		0.689		
Variance	0.014				

Rubin's method for determining the uncertainty of the imputed estimate was employed. Following this method, the total variance from the imputed datasets is $T = (\text{mean within-imputation variance}) + (1 + 1/(N \text{ sets of imputed datasets})) * (\text{between-imputations variance})$

= $0.689 + 1.1 * 0.014 = 0.704$. The SE^2 of the model conducted on the complete simulated dataset is 0.532. The ratio of these two values is $0.704/0.532 = 0.32$.

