So, the relative increase in variance due to missing values is 32%, indicating that $1.32 * 180$ subjects = 238 subjects are required to attain the same power that would be attained in a sample of 180 subjects who all complete the study. In other words, 238 subjects must be enrolled in the study, with 180 completing, to achieve the same power when using multiple imputation as would be achieved if 180 subjects were enrolled and all completed. If multiple imputation were not used, and only complete cases were analyzed, approximately 238 subjects would have to be enrolled to produce 180 complete cases. Thus, multiple imputation is more efficient than complete-case analysis, in addition to avoiding bias due to MAR missingness.

A secondary analytic approach will be to use mixed models on non-imputed data. Mixed models can be used to analyze repeated measures data without discarding subjects with missing data. Mixed models will be used for measures only obtained at pre- and post-assessment and on measures with interval assessments. Analytic approaches for each set of specific aims and hypotheses are detailed below.

Specific Aim 1: To conduct an RCT of an early dyadic intervention for PO-MDD, PCIT-ED, compared to a WL control condition.

Hypothesis 1A: Compared to those randomized to the WL, preschoolers who are first randomized to PCIT-ED will show significantly increased rates of remission, greater reductions in MDD symptoms, and decreases in impairment.

Hypothesis 1B: Compared to those randomized to the WL, preschoolers who are first randomized to PCIT-ED will show significantly greater increases in emotional competence measured by the ability to accurately identify emotions in themselves and others and the ability to effectively regulate intense emotions.

Hypothesis 1C: Compared to those on the WL, parents who are first randomized to PCIT-ED will show significantly greater increases in emotion skill learning (ESL) and reductions in MDD symptoms and parenting stress.

Analytic Approach: Continuous post-assessment scores will be compared between PCIT-ED and WL groups using analysis of covariance, covarying for pre-assessment scores. The stratification variables, gender and externalizing comorbid diagnoses, will also be included as covariates in the models.

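### The sample-size simulation applies Rubin's formula to results that were already pooled, a small conservative error; separately, 238 enrolled gives about 173 completers, not 180

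*Combined protocol and SAP*

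**What the plan says.** The sample-size part of the PCIT-ED Statistical Analysis Plan starts from a single simulated trial: "We assume N=90 completers in each group, so a simulated dataset with N=180 subjects was created". The simulated outcomes were drawn "assuming normally distributed scores with a SD of 4.69 (pooled SD from our pilot RCT"). The effect built into them was "a mean difference in change scores in the two groups of 2.5". Demographic profiles from the pilot were attached to the simulated cases at random. For drop-out, "we assume a 25% drop-out rate in the PCIT-ED group and a 30% drop-out rate in the WL group", and the missing values were chosen by random number, which the SAP itself describes as MCAR.

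On the imputation, the SAP says: "Multiple imputation was conducted 10 times, with 10 imputed datasets created". MIANALYZE was then "used to run a general linear model of change scores by group for each set of multiple imputed datasets". Table 5 gives one row for the complete simulated data and ten rows for the imputed data. Below the table the SAP reports that "Rubin's method for determining the uncertainty of the imputed estimate was employed". It averages the ten SE² values (0.689), calls this the within-imputation variance, takes the variance of the ten estimates (0.014) as the between-imputation variance, and forms 0.689 + 1.1 × 0.014 = 0.704. Dividing by the complete-data 0.532, it concludes that "the relative increase in variance due to missing values is 32" percent and that 238 must be enrolled, with 180 completing. It also gives about 238 as the enrolment needed without imputation, and then calls imputation the more efficient method.

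**The concern.** MIANALYZE is the pooling step. If it was run once per set of imputed datasets, each Table 5 row is already a Rubin-combined result, and its SE² holds both within- and between-imputation variance. Averaging those SE² values does not give a within-imputation variance. The scatter of the ten row estimates is then Monte Carlo variation between pooled results, and adding it counts between-imputation variation a second time.

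The 32% and the 238 both come from this calculation, as does the argument that imputation needs fewer subjects than a complete-case analysis. At stake are whether the enrolment target can be reproduced by a valid rule, and whether it delivers the number of completers that the SAP attaches to it.

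**Working it through.** **Inputs** (all from the SAP's simulation text and Table 5): 90 per group; SD 4.69; difference 2.5; drop-out 25% and 30%; complete-data SE² 0.532; ten row estimates, SE² and p-values. I use the SE² column throughout, because row 3's printed SE (0.569) does not match its SE² of 0.756 (√0.756 = 0.869, which does match t = -2.40).

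**1. The plan's figure reproduces.** Mean estimate -2.097; variance of the estimates 0.0139; mean SE² 0.689. T = 0.689 + 1.1 × 0.014 = 0.704. The ratio is 0.704/0.532 = 1.32 (printed as 0.32), and 1.32 × 180 = 237.6, so 238.

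**2. Were the rows already pooled?**

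- *Degrees of freedom.* A two-group model on one completed dataset of 180 has 178 df in every row. Solving each row's t (estimate/√SE²) and p for df gives:

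| Row | Implied df | p printed | p at 178 df |
|---|---|---|---|
| 1 | above 500, unstable to rounding | 0.0020 | 0.0023 |
| 2 | 132 | 0.0241 | 0.0237 |
| 3 | 94 | 0.0182 | 0.0173 |
| 4 | 116 | 0.0137 | 0.0132 |
| 5 | 213 | 0.0122 | 0.0123 |
| 6 | 364 | 0.0178 | 0.0183 |
| 7 | 162 | 0.0078 | 0.0077 |
| 8 | 136 | 0.0152 | 0.0149 |
| 9 | 110 | 0.0141 | 0.0135 |
| 10 | 185 | 0.0128 | 0.0128 |

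 Rows 1, 3, 4, 6, 8 and 9 are incompatible with 178. Rows 7 and 10 are compatible with it once rounding is allowed for. Rows 2 and 5 differ from 178 here, but not decisively if the rounded printed t is used.
- *Recovering the components.* Rubin's df is (m-1) × [T/((1+1/m)B)]². Assuming m = 10, row 3 gives 1.1B = 0.756/√(94/9) = 0.234, so W = 0.756 - 0.234 = 0.522 and B = 0.213. Over the ten rows W runs from 0.51 to 0.56 (mean 0.527, against the complete-data 0.532), and B averages 0.147.
- *Scatter between rows.* Estimates pooled over ten imputations should vary by about B/10 = 0.0147. Table 5 shows 0.014.
- *Simulation* (600 replicates of proper normal imputation, group plus six noise covariates, 22/90 and 27/90 missing). For single imputed datasets, the mean row SE² relative to the complete-data value has median 1.03 and 99.9th percentile 1.23; Table 5 has 1.295. The between-row variance relative to the complete-data value has median 0.36 and 0.1st percentile 0.054; Table 5 has 0.014/0.532 = 0.026. Both Table 5 values lie within the 1st to 99th percentile range for pooled sets of ten (1.16-1.76 and 0.008-0.096).

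**3. Without the second pooling.** 0.689/0.532 = 1.295; 1.295 × 180 = 233.1, so 233-234. The disputed term is 1.1 × 0.014 = 0.015 of variance, or about 5 subjects. If each set held ten imputations and all 100 were pooled once, T is about 0.675, the ratio about 1.27 and N about 229.

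**4. Separate check: completers from 238.** With 119 per group, 119 × 0.75 + 119 × 0.70 = 89.25 + 83.3 = 172.55, about 173. To obtain 90 completers per group needs 90/0.75 + 90/0.70 = 248.6, about 249.

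**5. Inflation expected under the simulation's own assumptions.** Randomly attached demographics cannot predict the outcome and the missingness is MCAR, so imputation recovers no information on average. The ratio expected is (1/67.5 + 1/63)/(2/90) = 1.38, and 1.38 × 180 is about 249. A result of 1.295 from one simulated dataset is ordinary chance: the ten row ratios alone run from 0.555/0.532 = 1.04 to 0.756/0.532 = 1.42.

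**6. Power** (two-sided 0.05, difference 2.5, SD 4.69, noncentral t). 90 + 90 completers: 0.945. 89.25 + 83.3 completers: 0.936.

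**The case against.** The strongest reply is that this hardly matters. The extra term is about 2% of the variance, it raises the target, and 233-234 of the 238 remain without it. That stands.

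The wording is also not clean. The SAP labels the rows as ten imputed datasets and never says how many imputations a set contained, so m = 10 is an inference. The fact that every row's SE² exceeds 0.532 would not prove pooling by itself; the evidence is the size of the excess, together with the df and the small scatter of the estimates. These limits stand too, but they do not restore the calculation. If the rows were single completed datasets, most of their p-values and the small between-row variance would be hard to explain.

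A reader might infer that the Rubin error left the trial under-enrolled. The documents do not support that, because correcting the error lowers the target. A reader might also take 1.38 as the inflation the trial must suffer, and 249 as the required enrolment. That does not follow either. The 1.38 is a no-information value for this simulation. The SAP intends to impute from all observed variables, and it collects interval measures such as the PFC-Scale at 6 and 12 weeks. If these predict the outcome, the inflation in the trial will be smaller.

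**Conclusion.** The second application of Rubin's formula is a methods error, shown by the SAP's account of how MIANALYZE was used and by most rows of Table 5. Its effect is small and conservative: 1.32 becomes about 1.295, and 238 becomes about 233-234 (about 229 if 100 imputations are assumed and pooled once).

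The completer statement is a distinct error with the opposite sign. At the stated drop-out, and assuming equal allocation, 238 enrolled gives about 173 completers. The loss of power is slight, from 0.945 to 0.936.

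The efficiency claim has no support in this simulation. Its predictors carry no information, it rests on one simulated dataset, and the SAP arrives at 238 with and without imputation. None of this shows an underpowered trial.

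**What to change.** Four changes of wording in the sample-size paragraphs:

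- Delete the second Rubin step, and state how many imputations each set held.
- Correct the 32% to about 29.5%, or replace it with an average over many simulated datasets. If 1.38 is quoted, describe it as the value when the imputation model has no predictive information.
- Keep 238, but state that at 25% and 30% drop-out it gives about 173 completers and two-sided power of about 0.936 for a 2.5-point difference with SD 4.69, against 0.945 with 180 completers.
- Withdraw the statement that this simulation shows imputation to be more efficient than complete-case analysis.

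The cost is redrafting about two paragraphs, plus a short simulation if the averaged figure is preferred. No change in enrolment is needed.

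### At the plan's own drop-out rates, 238 enrolled gives about 173 completers, not 180; the equal complete-case figure of about 238 cannot support the claim that imputation is more efficient

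*Combined protocol and SAP*

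**What the plan says.** All of this is in the sample-size paragraphs of the PCIT-ED Statistical Analysis Plan, between the description of multiple imputation and Specific Aim 1.

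- Starting point: "We assume N=90 completers in each group, so a simulated dataset with N=180 subjects was created".
- Drop-out: "we assume a 25% drop-out rate in the PCIT-ED group and a 30% drop-out rate in the WL group". Those shares of the simulated "MDD severity sum change scores were set to missing, respectively, using a random number generator".
- Predictors for the imputation: pilot demographic profiles, which "were drawn with replacement 180 times and randomly assigned to the 180 simulated cases".
- Result: Table 5 and Rubin's formula give a 32% increase in variance. Multiplying 180 by 1.32 gives 238, which the SAP first describes as the number needed to match the power of 180 subjects who all finish.
- Restatement: "238 subjects must be enrolled in the study, with 180 completing, to achieve the same power when using multiple imputation" as 180 enrolled and all completing.
- Comparison: without imputation, "approximately 238 subjects would have to be enrolled to produce 180 complete cases. Thus, multiple imputation is more efficient than complete-case analysis".

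**The concern.** Two sentences do not agree with the assumptions they rest on.

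The first makes 238 the enrolled number and 180 the completers. Those two numbers need less drop-out than the SAP assumes in either arm.

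The second gives complete-case analysis the same enrolment as imputation, then concludes that imputation needs less.

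A trial is monitored against its enrolment and completer counts. If drop-out ran exactly as assumed, this trial would finish about seven completers short of its stated 180 and look deficient while being on plan. A reader would also credit imputation with a saving that the printed figures do not show.

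**Working it through.** **Inputs, all from the SAP:** 90 per group; drop-out 25% (PCIT-ED) and 30% (wait list); mean difference in change 2.5; SD 4.69; Table 5. The 1:1 allocation of enrolled subjects is my assumption, suggested by the 90/90 design.

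**1. The plan's 238 reproduces.** From the ten imputed rows of Table 5, the mean squared SE is 0.689 and the between-row variance is 0.0139 (printed as 0.014).
- T = 0.689 + 1.1 × 0.014 = 0.704.
- 0.704 / 0.532 = 1.323, and 1.323 × 180 = 238.

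Two printing slips do not affect this. The ratio is printed as 0.32, which is its excess over 1. In row 3, SE 0.569 does not match squared SE 0.756, whose root is 0.869.

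**2. Completers among 238.**
- Implied drop-out: 1 − 180/238 = 24.4%, below both 25% and 30%.
- At 1:1: 119 × 0.75 + 119 × 0.70 = 89.25 + 83.30 = 172.6.
- Upper limit, with everyone in the lower-drop-out arm: 238 × 0.75 = 178.5.
- For 180 completers, 0.75x + 0.70(238 − x) = 180 gives x = 268 on PCIT-ED, more than the 238 enrolled.

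**3. Where the 180 comes from.** The SAP introduces the 180 simulated subjects as completers, then applies drop-out to those same 180. That leaves 90 × 0.75 + 90 × 0.70 = 130.5 with a score. So 180 is the sample before drop-out, and 1.32 × 180 is its enrolled equivalent. The SAP's first description of 238 is consistent with this; the restatement is not.

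**4. Complete-case enrolment.**
- Average drop-out at 1:1 is 27.5%, so 180 / 0.725 = 248.3.
- By arm: 90 / 0.75 = 120 and 90 / 0.70 = 128.6, so 120 + 129 = 249.
- By variance: (1/0.75 + 1/0.70) / 2 = 1.381, and 1.381 × 180 = 248.6.

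All three give about 248 to 249. As printed, the saving from imputation is 238 − 238 = 0. Against 248 to 249 it would be 10 to 11 subjects.

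**5. Whether the simulation could show a saving.** The SAP says of its own simulation: "Because the simulated missingness was random, missing values are not predicted by anything". The demographics were attached to cases at random, so they carry no information about the missing scores. The SAP itself makes the power gain from imputation conditional on predictors being useful. Here they are not, by construction. The no-gain benchmark is therefore the complete-case inflation of 1.38, and the gap between 1.38 and 1.32 in one dataset cannot be credited to imputation.

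**6. Effect on power.** For an unadjusted comparison of change scores, as in the simulation (normal approximation, two-sided 0.05), power = Φ(2.5/SE − 1.96).
- 90 and 90 completers: SE = 4.69 × √(1/90 + 1/90) = 0.699; power 0.947.
- 238 enrolled with no imputation gain, so 89.25 and 83.3: SE = 4.69 × √(1/89.25 + 1/83.3) = 0.715; power 0.938.

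**The case against.** The best defence is that 238 is soundly derived from Table 5, that the sentence before the restatement says what it means, and that the second 238 may be a misprint for 248. With 248 the conclusion would at least follow from the printed numbers. This is plausible, but the text cannot settle it. Correcting the misprint would leave the completer count wrong, and the simulation would still be unable to show a gain.

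Applying the 25% rate to everyone gives 180 / 0.75 = 240, close to the printed figure. That ignores the stated 30% on the wait list and leaves almost no saving.

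It is also fair to say that little turns on this. The chosen analysis does not change, and avoiding bias is a separate reason for imputation. Both points stand.

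A reader might infer more than the documents support:
- **That the trial is underpowered or should enrol more.** The power difference is about one point.
- **That imputation gives no precision in this trial.** The SAP says that "the analyst should use all observed variables available in predicting missing values", and the 6- and 12-week measures could be among them. The simulation used demographics only.
- **That 1.32 is itself an error, or that its rarity as a draw can be stated.** It follows from Table 5. How unusual it is depends on the exact imputation model and the pilot profiles, which the documents do not give.

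**Conclusion.** The point holds as a correction to two sentences. On the SAP's own rates, 238 enrolled yields about 173 completers at 1:1 and at most 178.5 under any allocation. The complete-case enrolment for 180 completers is about 248 to 249, not about 238. The efficiency conclusion does not follow as printed, and this simulation could not establish it even with the corrected figure.

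The impossibility of 180 completers does not depend on the allocation; the 173 does, as does the pooled 27.5%. The power comparison, about 0.94 against about 0.95, assumes no imputation gain and the SAP's difference and SD. It is for the unadjusted model of the simulation, not the analysis of covariance planned under Specific Aim 1. It shows a small practical effect, not an underpowered trial.

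**What to change.** In the sample-size paragraphs of the SAP:

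1. Say that 238 enrolled is expected to yield about 173 completers at the assumed drop-out, and that 180 is the fully observed sample whose power is being matched.
2. Correct the complete-case enrolment to about 248 to 249 for 180 completers in total.
3. Withdraw the efficiency claim as a conclusion of this simulation. Keep the bias rationale, and say that the actual imputation, using all observed variables, may gain precision.
4. State that 238 rests on one simulated dataset, that the no-gain benchmark of 1.38 corresponds to about 248 to 249, and that 238 without an imputation gain has about 0.94 two-sided power against about 0.95 for 180 completers. This gives an open basis for keeping 238.

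The printed ratio of 0.32 and the SE in row 3 of Table 5 can be corrected at the same time. The cost is SAP wording only, with no extra enrolment and no change to the analysis.

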TREATMENT (Immediate Treatment Randomization: ~Week 1-18 or Wait List Randomization: ~Week 18-36) During the treatment, parent and child will work with a therapist at the Early Emotional Development Program each week for 18 weeks. Each session will last approximately 1 hour, although there are a few weeks when sessions will last approximately 1.5-2 hours. During these sessions, parent and child will work with a therapist to improve their relationship, learn safe and effective disciplinary techniques, as well as both learn strategies to deal with a range of emotions. (See attached Sessions Manual) The therapist will assign homework and activities on a weekly basis. Parents will complete the ECBI prior to each session. Therapists will complete the DPICS, EDCI, TIC, OC-YC Screener, and Acceptance Inventory throughout the course of treatment.

INTERVAL A, B, C & D ASSESSMENTS (~ Weeks 6, 12, 24, 30) Either over the phone, at the Early Emotional Development Program, or via REDCap, parents will complete the HBQ-P Peer & Medication section, CBCL, PFC-Scale, BDI, PSI, CCNES and TAI. This will take approximately 1-1.5 hours to complete.

DISCONTINUATION

If at any point in the study the family decides to discontinue their participation, the research team will ask the parent to complete an Exit Questionnaire and potentially the parent and child to complete the Post 1 or Post 2 assessment if families are willing to do so.

LONG TERM FOLLOW UP

After the completion of planned study visits (Baseline, Post 1, and Post 2 assessments), the research team will contact families via phone and/or email with the contact information they provided us. This will be done in order to ensure up-to-date contact information. The research team will update their contact information in the REDCap database for future follow-up studies with this population. Participants can let us know if they would no longer like to be contacted for future studies and we will note that in the REDCap database and cease contact.

PCIT-ED Statistical Analysis Plan

All measures will be collected at pre- and post-treatment assessments (except EI). In addition, the HBQ-P (measuring symptom severity of all Axis I disorders and impairment), PFC-Scale, parent BDI-II, PSI, EDCI (measuring ESL in both groups) and will be collected at the 6- and 12-week assessments in both groups. In the PCIT-ED group, these interval assessments correspond to completion of the CDI and PDI modules.

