PFC-Scale and PAPA MDD severity sum scores will be used to assess differences in depressive symptoms; HBQ and PAPA impairment scores will be analyzed to determine differences in functional impairment. Differences in emotion regulation (as an executive function) in the two groups will be examined using scores from the BRIEF-P; emotion development will be analyzed using scores from the ERC, Emotion Understanding, FACE, KIDSEDF, and the "Waiting" and "Puzzle" tasks. Post-assessment EDCl, BDI-II, and PSI scores will be compared between PCIT-ED and WL groups to determine differences in increases in Emotion Skill Learning and reduction of parental depressive symptoms and parenting stress.

Rates of remission (defined by 50% reduction in MDD severity and not meeting diagnostic criteria) will be compared in the PCIT-ED and WL subjects using logistic regression.

Interval assessment scores will also be analyzed across PCIT-ED and WL groups in repeated measures mixed models. In these models, repeated measures of PFC-Scale, HBQ MDD and externalizing co-morbidity severity and impairment, PSI and ESL (measured by EDCl) at pre-assessment, 6-week assessment, 12-week assessment, and post-assessment will be compared between the PCIT-ED and WL groups.

In addition to the analyses described above, pre-assessment variables that could possibly be associated with outcome, such as subject age and maternal depression, will be investigated as potential predictors of outcome.

Specific Aim 2: To investigate mediators and moderators of treatment effects.

Hypothesis 2A: Parental emotion skill learning (ESL) will mediate treatment effects. Child depression outcomes will be mediated by parental ESL.

Hypothesis 2B: Parental Emotional Intelligence (EI, a stable trait measured at baseline by MSCEIT) will be a moderator of ESL and child outcome. Parents with higher EI will show better ESL, and as a result, children of parents with high EI will show better outcomes than children of parents with low EI.

Analytic Approach: Parental ESL will be measured with the Emotion Development Coding instrument. This is an itemized assessment of parents' emotion skill learning. Each item is rated as 3=satisfactory, 2=needs practice, or 1=not evident. The total ESL score will be calculated as the mean of these items.

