To assess parental ESL as a potential mediator of the relationship between treatment group and child treatment response, a macro (for SAS or SPSS) developed by Hayes will be utilized. For mediation analyses, the PROCESS macro estimates path coefficients in a mediation model and generates bootstrap confidence intervals for the indirect effects of the independent variable on the dependent variable through a mediator variable. It is also possible to include covariates not proposed to be mediators in the model. Paternal ESL will be evaluated by entering post ESL score into the model as a potential mediator, with treatment group as the independent variable and change in PAPA MDD severity sum score as the dependent variable.

Power for Mediation: To estimate power for this mediation analysis, the following steps were taken. First, we expect the difference in MDD severity sum change score in the two groups to be approximately 2.5, with a SD of 4.69 (based on our pilot study). With 90 subjects per group, an alpha of 0.05, and a 1-sided test, power=0.97. Next, we expect the correlation of change in MDD severity sum score and ESL score to be approximately 0.25. Using Fisher's Z transformation with a sample size of 180, the correlation of 0.25 transforms to $Z = \tanh(0.25) * \sqrt{180-3} = 3.398$. Subtracting 1.96 gives 1.438, corresponding to power=0.92. Thus, we will be well-powered to detect a mediation effect.

To assess parental emotional intelligence (EI) as a potential moderator of treatment response, the PROCESS macro will be used. For moderation analyses, the PROCESS macro

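### The remission logistic regression names no covariates, although the continuous outcomes are adjusted for the stratifiers and the baseline score; the covariate set should be prespecified

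*Combined protocol and SAP*

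**What the plan says.** The Analytic Approach for Specific Aim 1 opens with the continuous outcomes: "Continuous post-assessment scores will be compared between PCIT-ED and WL groups using analysis of covariance, covarying for pre-assessment scores". The next sentence adds: "The stratification variables, gender and externalizing comorbid diagnoses, will also be included as covariates in the models". The SAP then lists the continuous measures. Remission follows in a separate paragraph, which says that the rates "will be compared in the PCIT-ED and WL subjects using logistic regression". The endpoint is defined in the same sentence: "Rates of remission (defined by 50% reduction in MDD severity and not meeting diagnostic criteria"). That paragraph lists no covariates and does not call the model unadjusted.

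The paragraph after it plans repeated-measures mixed models for the interval scores, also without naming covariates. A last paragraph says that, in addition, "pre-assessment variables that could possibly be associated with outcome, such as subject age and maternal depression, will be investigated as potential predictors of outcome", but it gives no model.

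Baseline severity will be available: "All measures will be collected at pre- and post-treatment assessments (except EI").

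**The concern.** Remission is the first outcome listed in Hypothesis 1A, yet its model is less fully specified than those for the continuous outcomes beside it. Three things are at stake.

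- **Consistency with the design.** If gender and externalizing comorbidity stratified the randomization and also predict remission, a treatment-only model ignores the balance that stratification created. Its standard errors then tend to be slightly too large.
- **Efficiency.** A baseline value that may predict remission goes unused. The SAP offers no power figure for remission against which to judge the loss, and the main outcomes also face a Bonferroni correction (General Data Analysis Considerations).
- **Prespecification.** With the covariate list open, the analyst can choose among at least three models after seeing the data: group only, group plus strata, or group plus strata and baseline severity. The choice also changes what the odds ratio means, because adjustment turns a marginal odds ratio into a conditional one.

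**Working it through.** **1. What the SAP's own power figure covers.** The nearest stated figure is the 0.97 under Power for Mediation. Its inputs are a difference of 2.5, SD 4.69, 90 per group and one-sided alpha 0.05.

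z = 2.5 / (4.69 × √(2/90)) = 2.5 / 0.699 = 3.576; power = Φ(3.576 − 1.645) = Φ(1.931) = 0.973.

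This reproduces 0.97. A two-sided test would give Φ(3.576 − 1.960) = 0.947. The figure concerns change in MDD severity. The documents give no remission rate, odds ratio or power for the remission comparison.

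**2. Treatment-only benchmark for remission (rates assumed).** Two-sided 0.05, 90 per group, power = Φ[(Δ − 1.96·√(2p̄(1−p̄)/n)) / √((p₁(1−p₁)+p₂(1−p₂))/n)].

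- 20% vs 40%: (0.20 − 1.96 × 0.0683) / 0.0667 = 0.99, so power is 0.839.
- 30% vs 50%: (0.20 − 1.96 × 0.0730) / 0.0715 = 0.80, so power is 0.787.

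**3. Simulation of the three candidate models.** There were 3,000 trials per cell, N = 180, 1:1 allocation balanced within gender × externalizing strata, and a two-sided 0.05 Wald test. The sample size follows the SAP ("We assume N=90 completers in each group, so a simulated dataset with N=180 subjects was created"). Everything else is assumed: 50% in one gender category, 40% with externalizing comorbidity, no dropout, no Bonferroni, marginal remission rates held fixed, and prognostic odds ratios as shown (gender / externalizing / per SD of severity).

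| Rates | Prognostic ORs | Group only | + strata | + strata and severity | Full gain (points) |
|---|---|---|---|---|---|
| 20% vs 40% | 1 / 1 / 1 | 0.835 | 0.840 | 0.841 | 0.6 |
| | 1.2 / 1.5 / 1.3 | 0.826 | 0.832 | 0.840 | 1.4 |
| | 1.5 / 2 / 1.5 | 0.845 | 0.857 | 0.865 | 2.0 |
| | 1.5 / 3 / 2 | 0.849 | 0.868 | 0.893 | 4.4 |
| | 2 / 4 / 2.5 | 0.843 | 0.867 | 0.907 | 6.4 |
| 30% vs 50% | 1 / 1 / 1 | 0.773 | 0.779 | 0.774 | 0.1 |
| | 1.2 / 1.5 / 1.3 | 0.797 | 0.804 | 0.810 | 1.3 |
| | 1.5 / 2 / 1.5 | 0.789 | 0.805 | 0.817 | 2.8 |
| | 1.5 / 3 / 2 | 0.803 | 0.820 | 0.844 | 4.1 |
| | 2 / 4 / 2.5 | 0.812 | 0.841 | 0.876 | 6.4 |

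With prognostic covariates, the strata alone account for 0.6 to 2.9 points.

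**4. Error rates and standard errors.** Under the null, the treatment-only test rejected in 4.1% to 5.2% of trials (Monte Carlo SE about 0.4 points). Its model SE divided by its empirical SE was 0.97 to 1.04. The fully adjusted Wald test rejected in 4.6% to 6.1%. The 6.1% was in the most extreme row, so a little of the gain there reflects test size and not efficiency.

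**5. The actual endpoint.** Severity enters remission twice, and the two parts can pull in opposite directions. A high start makes it harder to fall below the diagnostic criteria, but regression to the mean can make a 50% drop easier. Simulating the composite endpoint with assumed inputs (baseline mean 10 to 12, SD 3; residual SD 4; diagnostic threshold 6 to 8; treatment difference 2.5) gave a remission odds ratio per SD of baseline severity between about 0.56 and 1.7, depending on the post-on-baseline slope. It was close to 1 for slopes of 0.3 to 0.6. Power simulations of the composite endpoint (N = 180, assumed inputs) showed adjustment gaining about 0.5 to 5 points and never losing any. Treatment-only null rejection was 3.7% to 5.2%.

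**6. Effect of leaving the choice open.** In 4,000 trials per cell with a true effect, the three models disagreed on significance in 4% to 13% of trials. Under the null, picking the most favourable of the three rejected in 6.1% to 7.0%.

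**7. Odds-ratio scale.** For 20% vs 40% the marginal odds ratio is (0.4/0.6)/(0.2/0.8) = 2.67. The matching conditional odds ratio ran from 2.73 to 3.40 as the covariates strengthened.

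**The case against.** The strongest reply is that the SAP never says the model is unadjusted. The stratifier sentence speaks of models in the plural and sits under the same Analytic Approach heading as the remission analysis. The SAP also chose logistic regression, which takes covariates, where Aim 3 uses a chi-square test. This has force: a reader might infer that the SAP specifies a treatment-only analysis, and the documents support that only as the more natural reading of a silent sentence. The reply covers the stratifiers alone, however. Baseline adjustment is stated for continuous scores only, and the paragraph on potential predictors is exploratory.

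A second reply is that the loss may be negligible. That is correct for weak covariates, as the table shows.

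A third is that comparing rates suggests a marginal contrast, which a conditional odds ratio does not give. This is a fair point about the estimand. It is a reason to report a standardized risk difference as well, and does not argue against adjusting.

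**Conclusion.** The point stands as a should-fix gap in specification with a modest statistical cost. No reading of the SAP puts baseline MDD severity in the remission model, and the natural reading leaves out the stratifiers too. Under the assumed rates and prognostic strengths, adjustment at 90 per arm gains from about 0 to 6 power points.

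Two stronger conclusions are tempting, and the documents do not support them.

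- **A large, certain power loss.** Gains of 4 to 9 points (for example 0.73 to 0.82) appear if the conditional log-odds ratio is fixed at 1.0 and odds ratios of 2.0 to 2.7 are assumed for each stratifier and 1.65 to 2.7 per SD of severity. The documents give none of these strengths. The composite-endpoint runs came nowhere near 2.7 for severity and leave even its direction open.
- **Materially wrong error bars.** The treatment-only test is at most slightly conservative, at about 4% to 5% Type I error. Any departure is in the safe direction, with no inflation of false positives.

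All power figures use two-sided 0.05 with neither Bonferroni correction nor dropout. They compare models and do not forecast the trial's power.

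**What to change.** Replace the remission sentence with: *Remission will be compared using logistic regression with treatment group, gender, externalizing comorbid diagnosis and baseline MDD severity score as covariates; the conditional odds ratio will be reported with a standardized (marginal) risk difference.* The severity score should be the one from which the 50% reduction is calculated. State also that the repeated-measures mixed models include the same two stratifiers.

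The cost is a line or two of SAP text, with no new data. The one small downside is that the odds ratio becomes conditional, which the standardized risk difference addresses. If the covariates turn out not to be prognostic, the simulations show no material loss from including them (0.835 vs 0.841, and 0.773 vs 0.774).
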